Pharmacogenetic sampling (optional) ^k		X							6.5.1
TC-5214 administration ^d			X						5.5.2
Blood sample collection for PK ^e			X	X	X	X	X		6.4.1.1
Urine sample collection for PK ^f			X	X	X	X	X		6.4.1.2
Dialysis Period / Dialysate Collection			X ^j						6.4.1.4
Discharge from clinic							X ^g		NA

Visit number	1	2 Residential Period (For Group 5, Part 1 – 2 Residential Periods)					3		
	Activity/ Day	-30 to -2 Screening	-1 ^h	1	2	3	4	Follow-Up 7 to 10 days following discharge	Details in Section
Concomitant medications	X	X	X	X	X	X	X		5.6
Adverse Events	X	X	X	X	X	X	X		6.3

^a Height will be measured during the screening visit only.

^b Orthostatic blood pressure and pulse will be measured at the Screening Visit, on Day -1 (time to correspond with the planned predose and 4 hour postdose timings for Day 1), on Day 1 at predose and 4 hours post dose, each morning during the residential period and at the Follow-up Visit.

^c Subjects must rest in the supine position for 10 minutes prior to the 12-lead ECG evaluation to be performed at screening, on admission on Day -1, on Day 1 at 4 hours postdose, before discharge on Day 4, and at the Follow-up Visit

^d Study drug will be administered with 240 mL room temperature water

^e For detailed timings of blood PK sampling times see Section 6.4.1.1.

^f Urine collection times for Groups 1 to 3: Urine will be collected for 72 hours postdose in the following intervals: 0-12, 12-24, 24-48 and 48-72 hours.

^g Subjects will be discharged from the unit after all study procedures have been completed.

^h Subjects may be admitted to the clinic on Day -2 for the Day -1 assessments at the discretion of the Investigator.

ⁱ Abbreviated physical examination.

^j Applies only to Group 5, Part 1, Treatment Period 2. Subjects will start their scheduled dialysis at 4 hours post TC-5214 administration. Dialysate will be collected over 1 hour intervals throughout the entire (approximately 4 hour) dialysis session (eg, 0 to 1, 1 to 2, 2 to 3, and 3 to 4 hours).

^k Subjects must agree to sign a separate, optional informed consent for genetic research in order for this sample to be collected.

Table 2: Study Plan, Part 2

Visit number	1	2 Residential Period							3	
	-30 to -2 Screening	-1 ^h	1	2	3	4	5	6	Follow-Up 7 to 10 days following discharge	Details in Section
Informed consent	X									8.4
Demography	X									6.2
Inclusion/exclusion criteria	X	X								4
Physical Examination	X	X ⁱ						X ⁱ	X	6.3.6

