Height and weight ^a	X	X						X		6.3.6
Medical and Surgical History	X									6.2
Columbia Suicide Severity Rating Scale	X	X						X	X	6.2
Clinical chemistry	X	X						X	X	6.3.5
Hematology	X	X						X	X	6.3.5
Urinalysis	X	X						X	X	6.3.5
HIV and HBV Serology	X									6.3.5
Drugs of Abuse Screen	X	X								6.3.5
Alcohol Screen		X								6.3.5
Blood pregnancy test for female subjects of childbearing potential	X	X						X		6.3.5

Visit number	1	2 Residential Period							3	
Activity/ Day	-30 to -2 Screening	-1^h	1	2	3	4	5	6	Follow-Up 7 to 10 days following discharge	Details in Section
Orthostatic blood pressure (supine, seated, and standing) and pulse ^b	X	X	X	X	X	X	X	X	X	6.3.7
Oral temperature and respiration rate	X	X	X	X	X	X	X	X	X	6.3.5
12-lead ECG ^c	X	X	X					X	X	6.3.6.1
Admission to the clinic		X								NA
Pharmacogenetic sampling (optional) ^j		X								6.5.1
TC-5214 administration ^d			X							5.5.2
Blood sample collection for PK ^e			X	X	X	X	X	X		6.4.1.1
Urine sample collection for PK ^f			X	X	X	X	X	X		6.4.1.2
Dialysis Period			X			X				6.4.1.4
Dialysate Collection						X ^j				6.4.1.4
Discharge from clinic								X ^g		NA
Concomitant medications	X	X	X	X	X	X	X	X		5.6
Adverse Events	X	X	X	X	X	X	X	X	X	6.3

- a Height will be measured during the screening visit only.
- b Orthostatic blood pressure and pulse will be measured at the Screening Visit, on Day -1 (time to correspond with the planned predose and 4 hour postdose timings for Day 1), on Day 1 at predose and 4 hours postdose, each morning during the residential period and at the Follow-up Visit.
- c Subjects must rest in the supine position for 10 minutes prior to the 12-lead ECG evaluation to be performed at screening, on admission on Day -1, on Day 1 at 4 hours postdose, before discharge on Day 6, and at the Follow-up Visit.
- d Study drug will be administered with 240 mL room temperature water.
- e For detailed timings of blood PK sampling times see Section 6.4.1.1.
- f Urine collection times: Urine samples for PK will be collected for 120 hours postdose in the following intervals: 0-12, 12-24, 24-48, 48-72, 72-96, and 96-120 hours. Urine will be collected for subjects in Part 2 for Groups 1 through 3, and for subjects in Group 5 who produce urine.
- g Subjects will be discharged from the unit after all study procedures have been completed.
- h Subjects may be admitted to the clinic on Day -2 for the Day -1 assessments at the discretion of the Investigator.
- i Abbreviated physical examination.

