6.3.6.1 Resting 12-lead ECG

The timing of ECGs are indicated in the study plans [Table 1](#) and [Table 2](#). A 12-lead ECG will be obtained after the subject has been resting in the supine position for at least 10 minutes. If indicated, additional ECG assessments can be made at the discretion of the Investigator. These assessments should be entered as an unscheduled assessment.

The Investigator will judge the overall interpretation as normal or abnormal. If abnormal, it will be decided whether or not the abnormality is clinically significant or not clinically significant and the reason for the abnormality will be recorded. All ECG readings will be stored as source documents both digitally and as a paper printout. The following variables will be reported: RR, PR, QRS, and QT intervals from the primary lead (V2) of the digital 12-lead ECG. The QTcF will be derived and reported.

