11. EVALUATION AND CALCULATION OF VARIABLES BY [REDACTED]

11.1 Calculation or derivation of safety variable(s)

All AEs will be collected for each subject from the time when informed consent is obtained (Visit 1) until the follow-up visit (Visit 3). AEs that occur before dosing will be reported separately.

Change-from-baseline variables will be calculated by [REDACTED] Inc for the safety variables listed below, as the posttreatment value minus the value at baseline. The baseline values will be as follows:

- Clinical laboratory tests: Day -1 value
- Vital signs (including supine blood pressure and pulse): Day -1 time-matched values
- ECG: Day 1

Baseline values for safety variables during each respective period will serve as the baseline value for that period.

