12.2.2 Safety

All safety data (scheduled and unscheduled) will be presented in the data listings.

Safety variables (ie, clinical laboratory values, vital signs, and ECGs) will be reported to the same precision as the source data. Derived variables will be reported using similar precision to those from which they were derived (eg, QT_c derived from QT interval).

Extra measurements (such as unscheduled or repeat assessments) will not be included in the descriptive statistics, but will be included in data listings. All AEs, ECG outliers, and clinical laboratory outliers that occur following the first dose of study medication will be included in the tabulations of AEs and outlier events, including episodes that occur at unscheduled evaluations.

All available data from subjects in the safety analysis set will be included in the safety analyses. No adjustment or imputation will be utilized for missing values or for subjects who withdraw prior to completing the study, neither will analyses be restricted to subjects with complete data.

All AEs will be collected for each subject when informed consent is obtained (Visit 1) until the follow-up visit (Visit 3). AEs that occur before dosing will be reported separately.

AEs will be summarized by preferred term and system organ class using MedDRA vocabulary (version 12.0 or higher) by treatment and across all treatments. Furthermore, listings of SAEs and AEs that led to withdrawal will be made and the number of subjects who had any AEs, SAEs, AEs that led to withdrawal, and AEs with severe intensity will be summarized.

Tabulations and listings of data for vital signs, clinical laboratory tests, ECGs, and physical examination findings will be presented. All continuous safety data will be summarized across all treatments for the absolute value at each scheduled assessment and for the corresponding change from baseline. For clinical laboratory tests, listings of values for each subject will be presented with abnormal or out-of-range values flagged. Clinical laboratory data will be reported in Système International units in the CSR.

For ECG parameters, the QT correction factor will be based on the Fridericia's formula. Further categorical summaries of absolute QT and QTcF values (greater than 450 ms, greater than 480 ms, greater than 500 ms) and change-from-baseline values in QT and QTcF values (greater than 30 ms, greater than 60 ms) may also be produced.

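### The ECG baseline is labelled Day 1, but the only ECG scheduled on Day 1 is 4 hours after dosing, so change from baseline in QTcF is zero or undefined at 4 hours and offset by the 4-hour effect afterwards

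*Supplement*

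**What the plan says.** Section 11.1 calculates change from baseline for safety variables "as the posttreatment value minus the value at baseline". It lists three baselines. Two precede the dose: "Clinical laboratory tests: Day -1 value" and "Vital signs (including supine blood pressure and pulse): Day -1 time-matched values". The third, for ECG, is given as Day 1 with no predose qualifier. The section adds that each treatment period uses its own baseline.

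Section 6.3.6.1 leaves ECG timing to the study plans: "The timing of ECGs are indicated in the study plans". Apart from screening, footnote c of Table 1 (Part 1) places ECGs "on admission on Day -1, on Day 1 at 4 hours postdose, before discharge on Day 4, and at the Follow-up Visit", and footnote c of Table 2 (Part 2) places them "on admission on Day -1, on Day 1 at 4 hours postdose, before discharge on Day 6, and at the Follow-up Visit".

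Section 12.2.2 summarizes all continuous safety data as absolute values and as change from baseline at each scheduled assessment. It also allows optional tables of QT and QTcF changes above 30 ms and above 60 ms, and of absolute values above 450, 480 and 500 ms.

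**The concern.** A baseline for a drug-effect measure should be free of drug. Read literally, Section 11.1 selects a value taken 4 hours after the dose. That is also the only scheduled ECG between dosing and discharge, so it is the one most likely to show an early effect. Making it the reference removes it from the change analysis and carries whatever effect it contains into every later change.

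Safety and tolerability in renal impairment compared with normal renal function is a secondary objective, and ECG is a named safety outcome. Change from baseline has particular use here because exclusion criterion 11 admits subjects with QTcF up to 500 ms by joint approval. Some may exceed the lower absolute thresholds before dosing, and a drug-free baseline is what separates that from a treatment effect.

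**Working it through.** The plan gives no figure to reproduce. The check sets the passages side by side and then follows the rule through.

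**Is there a scheduled predose Day 1 ECG?**
- Footnote b of the same tables gives blood pressure and pulse a predose time: "on Day 1 at predose and 4 hours postdose, each morning during the residential period and at the Follow-up Visit" (Part 2; Part 1 has the same times). Footnote c gives ECG none.
- Section 6 lets predose assessments be done up to 60 minutes before dosing, but it schedules no ECG.
- Section 6.3.6.1 allows additional ECGs at the Investigator's discretion, entered as unscheduled. Section 12.2.2 leaves unscheduled measurements out of the descriptive statistics.
- Amendment 1, as shown, does not revise Section 11.1.

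So none is scheduled.

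**What the rule computes.** Let E(t) be the true drug effect on QTcF at time t in a group.
- Day -1 baseline: reported change = E(t).
- 4-hour baseline: reported change = E(t) - E(4).
- Artefact = -E(4), the same at every later time and independent of elimination after 4 hours.
- At t = 4 the literal change is E(4) - E(4) = 0, or undefined if that record is treated only as baseline.

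**Illustration.** Assumptions, not taken from the documents: E(4) = 20 ms in every group, effect proportional to concentration, mono-exponential decline from 4 hours, and removal by dialysis ignored. The half-lives come from Section 3.2: 8 to 9 h, about 3-fold longer in moderate impairment (24 to 27 h) and about 10-fold longer in ESRD (80 to 90 h).

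Fraction of the 4-hour level left = 2^(-(t - 4)/half-life), with t - 4 = 68 h at 72 h and 116 h at 120 h.

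| Group | Fraction at 72 h | Fraction at 120 h | Literal change, 72 h | Literal change, 120 h | Day -1 baseline, 72 h | Day -1 baseline, 120 h |
|---|---|---|---|---|---|---|
| Normal | 0.003 to 0.005 | below 0.001 | -19.9 | -20.0 | +0.1 | 0.0 |
| Moderate | 0.14 to 0.17 | 0.035 to 0.051 | -16.5 to -17.2 | -19.0 to -19.3 | +2.8 to +3.5 | +0.7 to +1.0 |
| ESRD | 0.55 to 0.59 | 0.37 to 0.41 | -8.2 to -8.9 | -11.8 to -12.7 | +11.1 to +11.8 | +7.3 to +8.2 |

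Changes are in ms and scale linearly with E(4); at 10 ms they halve. At 4 hours the literal change is 0 in every group, against +20 with a Day -1 baseline.

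**Between groups.** The ESRD-minus-normal difference at 120 h is 7.3 to 8.2 ms under either baseline. At 72 h it is about 11.0 to 11.7 ms under either. With equal 4-hour effects the same 20 ms is removed from everyone and the comparison is unchanged.

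It changes only when E(4) differs. For example, suppose the 4-hour effect scales with dose, with 20 ms at 8 mg (normal) and 20 x 2/8 = 5 ms at 2 mg (ESRD). At 120 h the literal changes are -20.0 and about -3.0 to -3.2, a difference of about 17 ms. The Day -1 changes are 0.0 and about +1.8 to +2.0, a difference of about 2 ms. The distortion is 20 - 5 = 15 ms, exactly the difference in 4-hour effects.

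**The case against.** The best defence is that Day 1 is a slip for Day -1. The other two baselines in the list are Day -1. The flow-chart footnotes also say Day 1 for the time-matched assessments where the table footnotes say Day -1, and subtracting baseline from a posttreatment value presupposes a pretreatment baseline. This is plausible. But the text does not say so, and a predose Day 1 ECG is another possible meaning, so a programmer would have to guess.

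The consequences are also bounded, and this stands in full. AUC and Cmax are the primary variables, and no formal testing is planned. The tables above 30 and 60 ms are optional. Absolute QTcF values are still summarized and listed, the Investigator judges each ECG, and a sponsor medical expert reviews ECG data. The Day -1 ECG is collected, so no data are lost.

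Three stronger readings are tempting and are not supported:
- A reader might infer that slower elimination in ESRD makes the artefact differ between groups and creates a false gap from controls of some 7 to 12 ms. It does not. With equal 4-hour effects, that gap is the modelled residual drug effect and is identical under a Day -1 baseline.
- A reader might infer that no subject could have a predose Day 1 ECG. None is scheduled, but a discretionary one is possible.
- A reader might infer that a known QTcF effect would be concealed. The documents report none; the risk they name as most likely is orthostatic hypotension.

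**Conclusion.** The inconsistency is real and the stated rule gives a wrong result if followed. The change at 4 hours is lost, and each later change is shifted by minus the 4-hour effect, so a prolongation that wanes is reported as shortening. That follows from the subtraction alone, for any non-zero 4-hour effect. The millisecond figures rest on an assumed effect size and a simple decline model, and serve only as illustration.

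Distortion of the renal-group comparison is conditional: it requires 4-hour effects that differ between groups, which the 8 mg and 2 mg doses make possible but the documents do not show. Given the likely slip, the intact absolute summaries and the secondary role of ECG, this is a should-fix correction, to be made before the change-from-baseline tables are produced.

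**What to change.** In Section 11.1, replace the ECG baseline with the Day -1 admission ECG, taken from the same treatment period for Group 5 Part 1. State that the Day 1 4-hour ECG is the first postdose assessment, both in the change-from-baseline summaries and, if produced, in the Section 12.2.2 categories above 30 and 60 ms.

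The cost is one line of text with a matching clarification, and no new procedure. There are two small drawbacks to note when the results are read. The Day -1 ECG is not stated to be time-matched to the 4-hour recording, so within-day variation is not removed. In Group 5 subjects dosed after dialysis, it may also precede that session, so their 4-hour change may include an effect of dialysis itself.

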3.2 Rationale for study design, doses and control groups

The purpose of this study is to determine if renal impairment will affect the PK of TC-5214. The study is designed using the principals embodied in the Food and Drug administration guidance on drug renal impairment studies ([Cockcroft 1976](#)).

For control subjects with normal renal function and subjects with mild renal impairment, a 8 mg dose of TC-5214 was chosen because it is the highest daily dose that will be administered in Phase III trials and was shown to be well tolerated in healthy subjects in previous studies. For subjects with moderate and severe renal impairment, to minimize the effects of compensatory changes such as significant hypotension, a 2 mg dose will be administered.

In order to avoid bias due to demographic differences between the control subjects with normal renal function and subjects with renal impairment, the control group will be matched to the mean demographic characteristics of the **3** renal impairment groups with an allowable variability in age of +/- 10 years and in BMI of $\pm 3 \text{ kg/m}^2$. Sex will be matched to achieve similar distribution between male and female subjects. Only control subjects with stable chronic medical conditions will be included.

Based on available data to date, the mean terminal half-life ($t_{1/2,\lambda_z}$) of TC-5214 in human plasma is approximately 8 to 9 hours. Based on limited interim PK data in 2 subjects with moderate impairment, and 2 subjects with ESRD, renal impairment has been shown to increase the half-life of TC-5214 by approximately 3 and 10 fold, respectively.

For Groups 1 to 3, the study design has been updated to extend the sampling period to 120 hours postdose to adequately characterize the elimination phase of TC-5214 and more accurately determine TC-5214 PK parameters (eg $t_{1/2,\lambda_z}$, AUC, and CL/F). For Group 5 it was determined that a single dose of TC-5214 administered after the completion of a dialysis session, with the collection of blood samples for PK through 120 hours postdose (including a 4 hour dialysis session beginning approximately 72 hours postdose) would enhance patient safety.

The PK profile in patients with severe renal failure will be extrapolated from the data in subjects on dialysis obtained between their dialysis sessions, thus subjects with severe renal impairment (eGFR <30 mL/min) will not be recruited for this study.

4. SUBJECT SELECTION CRITERIA

Investigator(s) should keep a record, the subject screening log, of subjects who entered pre-study screening.

Each subject should meet all of the inclusion criteria and none of the exclusion criteria for this study. Under no circumstances can there be exceptions to this rule.

4.1 Inclusion criteria

For inclusion in the study subjects should fulfill the following criteria:

1. Provision of signed, written and dated informed consent prior to any study specific procedures.
2. Males and non-pregnant, non-lactating females 18 to 80 years old inclusive with suitable veins for cannulation or repeated venipuncture
 - Male subjects: Male subjects who are sexually active must be willing to use accepted double barrier method of contraceptive methods (eg condom or diaphragm plus spermicide), avoid unprotected sex, and avoid donating sperm until 3 months after drug administration.
 - Women of childbearing potential: Women of childbearing potential must have a negative blood pregnancy test confirmed by the Investigator, and use a highly effective form of birth control for 3 months before enrollment and until 3 months after their last dose of study drug. The following methods of highly effective birth control include vasectomized sexual partner, tubal occlusion, intra-uterine device (copper banded coils only), intrauterine system (eg, Mirena), Depo-Provera, implants (Implanon, Norplan), normal and low dose combined oral pills, ethinylestradiol transdermal system (Evra Patch), and intravaginal device (NuvaRing). Highly effective birth control can also include true sexual abstinence (starting at the screening visit and through completion of the study) or a double barrier method of contraception (eg diaphragm plus spermicide). The Investigator will capture the method of birth control and compliance at each study visit.
 - Women of non childbearing potential: Women of non childbearing potential are defined as women who are either permanently sterilized (hysterectomy, bilateral oophorectomy, or bilateral salpingectomy but excluding bilateral tubal occlusion) or who are postmenopausal. Women will be considered post menopausal if they are amenorrheic for 12 months without an alternative medical cause. The following age-specific requirements apply:

Women under 50 years old would be considered post menopausal if they have been amenorrheic for 12 months or more following cessation of exogenous hormonal treatment, and LH and FSH levels in the post-menopausal range.

Women over 50 years of age would be considered postmenopausal if they have been amenorrheic for 12 months or more following cessation of all exogenous hormonal treatment.
3. Regarding renal function, subjects will be classified as either normal or as suffering from mild, moderate or severe renal impairment. Classification of renal impairment

will be based using an abbreviated 4 variable MDRD equation. To ensure the assessment of consistent estimated glomerular filtration rate (eGFR) using the MDRD, a single equation will be used (see Section 6.2)

4. Have a body mass index (BMI) between 19 and 40 kg/m² and weigh at least 50 kg.
5. Be able to understand and comply with the requirements of the study as judged by the Investigator.

For inclusion in the genetic component of the study, subjects must fulfill the following additional criterion:

6. Provision of signed, written and dated informed consent for genetic research. If a subject declines to participate in the genetic component of the study, there will be no penalty or loss of benefit to the subject. The subject will not be excluded from other aspects of the study described in this Clinical Study Protocol, so long as they consent.

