^b A single dose of TC-5214 8 mg will be administered for Groups 1 and 2, 2 mg will be administered for Groups 3 on Day 1.

^c Subjects may be admitted to the clinic on Day -2 to allow for the Day 1 time-matched safety assessments at the discretion of the Investigator.

[figure not shown]
^d For subjects in Groups 1 through 3, during Part 1 blood and urine samples are collected through 72 hours postdose, and for Part 2, blood and urine samples are collected through 120 hours postdose.

Figure 2: Study Flow Chart Group 5, Part 1

- ^a Visit 1 may be conducted over 1 or more days during the screening period.
- ^b A single dose of TC-5214 2 mg will be administered to Group 5 on Day 1 of each residential period
- ^c Subjects may be admitted to the clinic on Day -2 to allow for the Day 1 time-matched safety assessments at the discretion of the Investigator.
- ^d At least 14 days between TC-5214 administrations.

Figure 3: Study Flow Chart Group 5, Part 2

- ^a Visit 1 may be conducted over 1 or more days during the screening period.
- ^b A single dose of TC-5214 2 mg will be administered to Group 5 on Day 1.
- ^c Subjects may be admitted to the clinic on Day -2 to allow for the Day 1 time-matched safety assessments at the discretion of the Investigator.

Table 1: Study Plan, Part 1

Visit number	1	2 Residential Period (For Group 5, Part 1 – 2 Residential Periods)					3		
	Activity/ Day	-30 to -2 Screening	-1 ^h	1	2	3	4	Follow-Up 7 to 10 days following discharge	Details in Section
Informed consent	X								8.4
Demography	X								6.2
Inclusion/exclusion criteria	X	X							4
Physical Examination	X	X ⁱ					X ⁱ	X	6.3.6
Height and weight ^a	X	X					X		6.3.6
Medical and Surgical History	X								6.2
Columbia Suicide Severity Rating Scale	X	X					X	X	6.2
Clinical chemistry	X	X					X	X	6.3.5
Hematology	X	X					X	X	6.3.5
Urinalysis	X	X					X	X	6.3.5
HIV and HBV Serology	X								6.3.5
Drugs of Abuse Screen	X	X							6.3.5
Alcohol Screen		X							6.3.5

Visit number	1	2 Residential Period (For Group 5, Part 1 – 2 Residential Periods)					3		
	Activity/ Day	-30 to -2 Screening	-1 ^h	1	2	3	4	Follow-Up 7 to 10 days following discharge	Details in Section
Blood pregnancy test for female subjects of childbearing potential	X	X					X		6.3.5
Orthostatic blood pressure (supine, seated, and standing) and pulse ^b	X	X	X	X	X	X	X	X	6.3.7
Oral temperature and respiration rate	X	X	X	X	X	X	X	X	6.3.5
12-lead ECG ^c	X	X	X				X	X	6.3.6.1
Admission to the clinic		X							NA

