10. Abstain from blood or plasma donation until 3 months after the final medical examination at the study follow-up.
11. Abstain from unprotected sex and sperm donation from the first administration of IP until 3 months after the last administration of IP. Subjects should ensure that their partners of child bearing potential use a reliable method of contraception.

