6.2.1 Follow-up procedures

A poststudy medical examination will be performed 7 to 10 days after the final discharge from the study site. This will be similar to the one performed at screening and will include a complete physical examination, vital signs, recording a 12-lead paper ECG, a blood sample for clinical chemistry, hematology, a urine sample for urinalysis, CSSRS, and assessment of any AEs or required medication.

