6.3.5 Laboratory safety assessment

Blood and urine samples for determination of clinical chemistry, hematology, serology, and urinalysis will be taken at the times indicated in the study plan [Table 1](#) and [Table 2](#). The date and time of collection of all laboratory tests will be recorded.

The following laboratory variables will be measured:

Clinical chemistry

Serum (S)-Albumin
S-Bilirubin, direct
S-ALT
S-AST
S-Alkaline phosphatase
S-Bilirubin, total
S-Bilirubin, direct
S-Blood Urea Nitrogen
S-Chloride
S-Creatinine
S-GGT
S-Protein, Total
S-Potassium
S-Sodium
S-Uric Acid

Hematology

Blood (B)-Hemoglobin
B-Leukocyte
B-Absolute leukocyte differential count
B-Platelet count
B-Red blood cell count
B-Hematocrit

Urinalysis

Urine (U)-Appearance
U-Bilirubin
U-Blood
U-Glucose
U-Ketones
U-Nitrites
U-pH
U-Protein
U-Specific Gravity
U-Urobilinogen

If a urine sample is positive for protein or blood, a microscopic examination of the urine sediment will be performed. Urine safety samples will not be required for anuric subjects.

Additionally, at screening all subjects will be tested for HIV and hepatitis B surface antigen. Subjects will be tested for alcohol using either blood test or a breathalyzer. Subjects will be tested for the following drugs of abuse on admission to the clinic using urine, blood, or saliva samples: amphetamines, barbiturates, cocaine, oxycodone, and tetrahydrocannabinol. For female subjects, a urine or blood pregnancy test will be performed at screening, on admission and at final discharge. The method for ethanol, drugs of abuse, and the pregnancy assessments will be recorded in the pCRF. If a subject tests positive to any of these screening tests he/she will be excluded from the study (except for subjects who are on prescription medications, which are verified by the Investigator).

Laboratory values outside the reference limit (other than those associated with the subject's degree of renal impairment and /or stable chronic condition) suspected to be of any clinical

significance will be repeated. Subjects, in whom suspected clinical significance is confirmed will either not be included or if they have already received treatment, will be followed until normalization or for as long as the Investigator considers necessary. Additional laboratory variables may be performed for safety reasons if judged appropriate by the Investigator.

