9.5 Study timetable and end of study

The end of the study is defined as 'the last visit of the last subject undergoing the study'.

The study is expected to start in the [REDACTED] and to end by the [REDACTED].

The study may be terminated at individual centers if the study procedures are not being performed according to GCP, or if recruitment is slow. AstraZeneca may also terminate the

entire study prematurely if concerns for safety arise within this study or in any other study with TC-5214.

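### Inclusion criterion 2 sets contraception to 3 months after the last dose, but the same bullet gives abstinence a different end date that is not tied to dosing

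*Supplement*

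**What the plan says.** The bullet on women of childbearing potential in inclusion criterion 2 (Section 4.1) opens with a general duty: they must "use a highly effective form of birth control for 3 months before enrollment and until 3 months after their last dose of study drug". A list of acceptable methods follows, none with a date. The bullet then says: "Highly effective birth control can also include true sexual abstinence (starting at the screening visit and through completion of the study".

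Four other places bear on the point:

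- Section 5.1, restriction 11: "Abstain from unprotected sex and sperm donation from the first administration of IP until 3 months after the last administration of IP".
- Section 6.2.1: "A poststudy medical examination will be performed 7 to 10 days after the final discharge from the study site". This is the subject's last scheduled visit.
- Section 9.5 defines the end of the study as "the last visit of the last subject undergoing the study".
- Section 13.3.1 states that women of childbearing potential may not be included at all.

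**The concern.** One bullet gives two end dates for the same obligation. A site with an abstinent participant could take the specific parenthesis to override the general clause before it, and tell her that her obligation ends at her last visit. A woman using any other listed method would be told 3 months. The start dates differ as well. What is at stake is whether sites apply one contraception rule consistently. The PK comparison is not touched.

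**Working it through.** The plan states no figure for this gap, so the check is a comparison of texts plus a day count.

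**1. Is the clause live?** Section 13.3.1 would make it moot if it governed. However, criterion 2 admits these women on conditions. Both study plans (Tables 1 and 2) carry a row headed "Blood pregnancy test for female subjects of childbearing potential", and Section 6.3.5 states: "For female subjects, a urine or blood pregnancy test will be performed at screening, on admission and at final discharge". The eligibility section and the schedules agree that they can enrol. Section 13.3.1, in the pregnancy-reporting part of the protocol, is the outlier.

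**2. End date if completion is the subject's own follow-up visit.**

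Inputs: dose on Day 1; discharge on Day 4 in Part 1 and Day 6 in Part 2 (Section 3.1, Tables 1 and 2); follow-up 7 to 10 days after final discharge (Section 6.2.1). For Group 5 in Part 1, the count starts from the second dose, with discharge on Day 4 of that period as in Table 1. Three months is taken as 91 days (90 to 92, depending on the calendar).

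Days from last dose to follow-up = (discharge day − 1) + 7 to 10.

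| | Discharge after dose | Follow-up after dose | Share of 91 days | Shortfall |
|---|---|---|---|---|
| Part 1 | 4 − 1 = 3 days | 10 to 13 days | 10/91 = 11% to 13/91 = 14% | 91 − 13 = 78 to 91 − 10 = 81 days |
| Part 2 | 6 − 1 = 5 days | 12 to 15 days | 12/91 = 13% to 15/91 = 16% | 91 − 15 = 76 to 91 − 12 = 79 days |

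Across both parts the shortfall is 76 to 81 days, or 76/7 = 10.9 to 81/7 = 11.6 weeks. With 90 or 92 days for 3 months, the outer limits become 90 − 15 = 75 and 92 − 10 = 82 days.

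**3. End date if completion is the trial-level end in Section 9.5.** The date then depends on when the last subject finishes. Suppose that subject is in Part 2 and is dosed D days after the woman in question. Her abstinence period then ends D + 12 to D + 15 days after her own dose. It reaches 91 days only if D is at least 91 − 15 = 76 to 91 − 12 = 79 days. Women dosed well before the last subject could have a longer period than 3 months. Women dosed near the end would have a shorter one, and for the last subject herself it is 12 to 15 days. The study dates are redacted, so this reading cannot be sized further.

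**4. Start date.** The main clause asks for birth control for 3 months before enrolment. The parenthesis starts abstinence at screening, which Section 6.2 places within the 30 days before admission. Section 6.2 also equates enrolment with Visit 1, the screening visit. On that footing an abstinent woman is asked for none of the 3 preceding months. If enrolment were instead taken as admission, she is asked for at most 30 days.

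Neither reading of completion ties the end of abstinence to 3 months after the last dose, and the start does not match either.

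**The case against.** The strongest reply is that the governing duty is clear. The main clause says these women must use highly effective birth control to 3 months after the last dose. The abstinence sentence only says what can count as a method, so a woman who stops being abstinent would have to move to another listed method. Restriction 11 points the same way. A site releasing her at follow-up would have to disregard the main clause, and would leave restriction 11 in force.

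Much of this stands, and it limits the size of the point. It does not remove the contradiction. Abstinence is the only method given its own dates, and nothing says that a switch is required. Restriction 11 bars unprotected sex, which is less than requiring a highly effective method, and it does not amend an eligibility criterion.

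Three stronger readings are tempting, and the documents do not support them:

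- **No rule applies after the follow-up visit.** The main clause and restriction 11 both run to 3 months.
- **The end of study is undefined.** Section 9.5 defines it at trial level. The narrower point is that the parenthesis is not tied to that definition or to any subject-level date.
- **The parenthesis leaves abstinent women unmonitored.** Contraceptive compliance is recorded only at study visits and the last pregnancy test is at final discharge, but this holds for every method and would be unchanged by mending the parenthesis.

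**Conclusion.** The contradiction is real and minor. Read at subject level, the abstinence period ends about 10 to 15 days after the last dose, roughly 11 weeks before the 3-month standard in the same bullet. This size rests on three assumptions: completion means the subject's own follow-up visit, discharge and follow-up occur as scheduled, and 3 months is about 91 days. On the trial-level reading a shortfall is certain only for subjects dosed late, and the period may be longer than 3 months for others.

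A reader might go on to infer a risk of fetal exposure. The documents give no exposure threshold that would support this, and the point does not depend on it. It concerns consistent wording of a participant-protection rule, and no primary or secondary PK result is affected.

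**What to change.** In criterion 2, make the abstinence period run to 3 months after the final dose. Alternatively, state that a woman who ends abstinence sooner must use another listed method for the remainder of the 3 months. In the same sentence, bring the start of abstinence into line with the requirement for 3 months before enrolment, or say why starting at screening is enough. Changing the end date alone would leave that mismatch in place.

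Correct Section 13.3.1 to say that women of childbearing potential may enrol only if they meet the contraception conditions of criterion 2.

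The cost is a small wording change in each of two sections, made by amendment with the usual ethics approval. Aligning the start date could make a woman ineligible if she had not been abstinent, or on another listed method, for the preceding 3 months; the main clause already requires this. Sample size, visits, sampling and analysis do not change.
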